Open repair of thoracoabdominal aneurysms, especially in patients with preexisting comorbidities, is fraught with complications. A meta-analysis of 7,833 open repairs of thoracoabdominal aneurysm repairs from 2000 to 2010 found a 30 day mortality rate of 7%, in-hospital mortality of 10%, spinal cord ischemia rates of 7.5%, renal failure rates of 19%, and pulmonary dysfunction rates of 36%²¹. Predictors of adverse events after elective open repair based on pre-existing comorbidities have been established. Advanced age (>70 years)²²⁻²⁵, respiratory disease²⁴, renal insufficiency²⁶, coronary artery disease^{22,25}, symptomatic aneurysms, extent 1 and 2 aneurysms²⁷⁻³⁰, and diabetes³¹ are reported to be a predictor of 30-day mortality. Cardiac function³², extent 1 and 2 aneurysms^{28,33-35}, symptomatic cases³⁵, and diabetes³¹ are reported to be predictors of paraplegia. The outcomes reported above are in a low- to moderate- risk patient population. It is a logical extension to assume the outcomes in moderate- to high- risk patients would be worse.

Open Surgical Repair of Ruptured, Urgent, and Emergent TAAAs

Open repair of any thoracoabdominal aneurysms, especially in patients with preexisting comorbidities, is fraught with complications. A recent review of emergent patients with a ruptured TAAA looked at the overall mortality of 51 emergently treated patients with TAAA between 1994 and 2014. The study evaluated Crawford Type I, II, III, and IV presenting hemodynamically unstable (94%) and hemodynamically stable (3%). In this study 54.9% (28/51) had true aneurysms and 45% (23/51) had dissecting aneurysms. These were further broken into 94% (48/51) that presented emergently requiring treatment in 2-6 hours and 6% (3/51) that presented urgently and required treatment within 24 hours. The overall mortality in this study was 43% (23/51); 15% (8/51) of these occurring during the procedure and 27% (14/51) occurred post-operatively. Of the 84% (43/51) that survived the initial procedure, 16% (6/42) developed paraplegia/paraparesis, 18.6% (8/43) had acute renal failure, 35% (15/43) had pulmonary insufficiency, and 18.6% (8/43) with post-operative bleeding. The average visceral ischemic time was 36 minutes and the average blood loss was 2875cc¹⁴.

Open Surgical Repair of Chronic Type B Dissections

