The primary purpose of this study is to evaluate the safety of this device as there are no or very limited devices and clinical options available for this patient population. The primary safety endpoint of this study is freedom from major adverse events (MAE) at 30 days or during hospitalization if this exceeds 30 days. Major adverse events include death, bowel ischemia, myocardial infarction, paraplegia, renal failure, respiratory failure, and stroke. The primary safety endpoint will be analyzed to determine statistical significance when compared to a target performance goal. A literature review of outcomes of open surgical repair was used to create the performance goal as there is not a comparable endovascular option to use for analysis. The performance goal was selected based on the range of subjects experiencing a major adverse event at 30 days. The range was calculated based on assumptions of the minimum and maximum number of subjects experiencing at least one MAE in the historical open surgical repair group (Table 6). Based on the literature reviewed and the above assumptions the range of subjects experiencing at least one MAE in the open surgical repair group is 30.5% to 77.4%.

The primary effectiveness endpoint is the proportion of the study subjects with treatment success at 1 year. Similarly, the data will be presented as quality outcomes with the number of study subjects with treatment success compared to the overall patient population.

The primary non-technical endpoint is patient quality of life domains at one year by SF36 testing at one year, and other follow-up intervals.

Additionally, data outcomes from this study will be entered into a common vascular database so that data can be pooled with other PS-IDEs. This would provide consistent reporting across the PS-IDEs. Additionally, the PS-IDEs will be evaluating the same device and endpoints to allow for a pool-ability of data across the sites. The data will be separated into two separate study arms: primary study arm and expanded selection arm. The primary cost related outcomes are total, global healthcare costs from time of surgery to one year after treatment with the Valiant Thoracoabdominal Stent Graft System.

Statistical Methods

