The primary hypothesis of the Visceral Manifold Study is the number of subjects experiencing a major adverse event through 30 days will be less than a target performance goal (PG) of 50%. The PG was determined by using a conservative target that is approximately the average of the open surgical repair MAE rate calculated above (30.5%-77.4%, Table 6). The anticipated test device 30 day MAE rate was based on the current rate of MAE's (26%, Table 7) observed in 20 subjects meeting inclusion criteria into the primary study as of June 2016.

The sample size for the Visceral Manifold Study was determined using an exact method based on a one-sided 2.5% significance level and an anticipated 26% investigational device 30 day major adverse event rate. Based on these assumptions, a sample size from the pooled PS-IDE data of 46 subjects provides at least 80% power to test the primary hypothesis.

Table 6. Historical Comparison for Primary Safety Endpoint (MAE Rate at 30 days for Open Repair)

Reference	# of Patients	Mortality	Bowel Ischemia	Myocardial Infarction	Paraplegia	Renal Failure	Respiratory Failure	Stroke
Rigberg et al	1010	191 (19%)						
Becquemin et al	1678	90 (5.4%)	51 (3%)	20 (1.2%)	16 (1%)	289 (17.2%)	124 (7.4%)	12 (0.7%)
Murana et al	542	46 (8.5%)			22 (4.2%)			
Ferrer et al	257	16 (6.2%)			53 (20.8%)	31 (12.3%)	31 (12.3%)	
Bensley et al	450	45 (10%)		10 (2.4%)		48 (10.7%)	202 (45.1%)	9 (2.2%)
Nathan et al	83	6 (5.6%)						
Dayama et al	682	68 (10%)		87 (12.9%)		117 (17.2%)	286 (42%)	
Ferrante et al	200	5 (2.5%)		25 (12.8%)		22 (11%)	27 (13.8%)	
Tsilimparis et al	1091	58 (5.4%)		87 (8%)		109 (10%)	229 (21%)	
Piazza et al	7833	1331 (17%)			587 (7.5%)	1488 (19%)	2819 (36%)	
Total	13826	1855/13826	51/1678	229/4101	678/10310	2104/12191	3718/12191	21/2128
Rate of MAE at 30 Days for Open Surgical Repair		13.4%	3.0%	5.6%	6.6%	17.3%	30.5%	1.0%

Table 7. Historical Comparison for Expected Investigational Device 30 Day MAE Rate (Outcomes of subjects treated with the Visceral Manifold System and meeting inclusion into the primary study as of June 2016)

Dataset	Mortality	Bowel Ischemia	Myocardial Infarction	Paraplegia	Renal Failure	Respiratory Failure	Stroke
Subjects meeting VMS PS-IDE I/E criteria	0/20 (0%)	0/20 (0%)	0/20 (0%)	2/20 (9.5%)	1/20 (5%)	3/20 (14%)	0/20 (0%)

Limitations of the Study

Limitations of the study are that it is a single center study with a small patient population.

Risk Analysis

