Major adverse events: all-cause mortality, bowel ischemia (requiring medical or surgical management), myocardial infarction, paraplegia, renal failure, respiratory failure, and stroke

- **All-Cause Mortality:** any death occurring within the first 30 days post procedure
- **Bowel Ischemia:** Bowel ischemia due to limb or arterial occlusion, graft placement, or embolization.
- **Myocardial infarction:** raised levels of cardiac biomarkers or ECG changes
- **Paraplegia:** spinal cord ischemic event resulting in complete loss of motor function with or without loss of sensation in the lower extremities
- results in a serum creatinine >2.0 mg/dl that does not spontaneously resolve
- **Renal Failure:** acute or progressive renal insufficiency leading to the need for dialysis or hemofiltration
- **Respiratory failure:** ventilator support >24 hours after spinal drain removal and/or reintubation. This definition does not put the patient at any increased risk. The high risk patient population being treated in this study is prone to pre-existing comorbidities, including COPD and decreased respiratory function, and may require extended ventilator support while in the supine position for spinal drainage.
- **Stroke:** neurological deficit that lasts > 24 hours

Malperfusion of organ(s) or limb(s): loss of flow through a particular vascular bed has been partially or completely compromised leaving the said organ or limb ischemic

Migration, clinically significant: antegrade or retrograde migration that requires surgical or endovascular intervention

Paraparesis: spinal cord ischemic event resulting in partial neurologic deficit in the lower extremities

Parietal arteries (branches): inferior phrenic, lumbar and middle sacral arteries

Patency: the state of a vessel that has unimpeded flow into and out of the vessel

Proximal landing zone: the aortic fixation site closest to the heart

Proximal fixation length: the aortic fixation site measured from the proximal edge of the graft to the start of the aneurysm

Renal insufficiency: rise in serum creatinine of more than 50% above pre-procedure level which results in a serum creatinine >2.0 mg/dl that does not spontaneously resolve

Technical success:

- successful delivery (i.e., ability to deliver the implant to the intended implantation site, without the need for unanticipated corrective intervention related to delivery);
- successful and accurate deployment, defined as:

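### Table 6 files the largest open-repair source's spinal cord ischemia and pulmonary dysfunction as paraplegia and respiratory failure, so calling the 50% performance goal conservative is unsupported

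*Combined protocol and SAP*

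**What the plan says.** The primary hypothesis (section 7.C, Statistical Methods) is that the number of subjects with a "major adverse event through 30 days will be less than a target performance goal (PG) of 50" per cent. The goal is described as a "conservative target that is approximately the average of the open surgical repair MAE rate calculated above (30.5%-77.4%, Table 6". The Data Presentation and Analysis Plan states that "the range of subjects experiencing at least one MAE in the open surgical repair group is 30.5% to 77.4" per cent.

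The largest row of Table 6, with 7,833 of 13,826 patients (57%), reads "Piazza et al 7833 1331 (17%) 587 (7.5%) 1488 (19%) 2819 (36" per cent. It enters 587 (7.5%) under Paraplegia and 2,819 (36%) under Respiratory Failure. Section 3 (Open Surgical Repair) reports the same 7,833 repairs as having "spinal cord ischemia rates of 7.5%, renal failure rates of 19%, and pulmonary dysfunction rates of 36" per cent. The Open Surgical Repair paragraph under Benefits and Risks of Treatment Options repeats those labels.

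The Definitions section sets what counts as an MAE in this trial:
- Paraplegia: "spinal cord ischemic event resulting in complete loss of motor function with or without loss of sensation in the lower extremities".
- Respiratory failure: "ventilator support >24 hours after spinal drain removal and/or reintubation".
- Paraparesis: "spinal cord ischemic event resulting in partial neurologic deficit in the lower extremities". This is not an MAE component. Freedom from paraparesis at 30 days is a separate secondary endpoint.

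**The concern.** A performance goal is a fair threshold only if the historical rate and the device rate count the same events. Here two cells change label between the Background and Table 6, and no explanation or adjustment is given.

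For the spinal cell, the mismatch can be shown from the protocol itself. Its definitions treat both complete and partial deficits as spinal cord ischemic events, but only the complete form is an MAE.

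For the respiratory cell, the trial's definition is narrow. Ventilation is counted only from spinal drain removal, and Post-operative Care keeps patients with a drain in bed for 48 to 72 hours where possible. Nothing shows that the source scored pulmonary dysfunction this way.

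At stake is the threshold of the plan's one formal safety test. If the comparator includes events that the device patients are not charged with, the goal is easier to beat than it appears.

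**Working it through.** **Inputs.** Table 6 totals: mortality 1,855/13,826; bowel ischemia 51/1,678; myocardial infarction 229/4,101; paraplegia 678/10,310; renal failure 2,104/12,191; respiratory failure 3,718/12,191; stroke 21/2,128. From Statistical Methods: exact test, one-sided 2.5%, device rate 26%, 46 pooled subjects. The mortality entry of the 7,833-repair source is left as printed throughout, since it is a separate question.

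**The plan's own figures.** The text does not spell out the rule, but this one reproduces them:
- Lower bound = largest pooled component = respiratory failure = 30.5%.
- Upper bound = sum of the components = 13.4 + 3.0 + 5.6 + 6.6 + 17.3 + 30.5 + 1.0 = 77.4%.
- Midpoint = (30.5 + 77.4)/2, or 53.9% from unrounded rates. The goal is 50%.
- Exact test, n = 46, goal 50%: success at 15 or fewer events; attained alpha 1.3%; power at 26% = 88.1%. The claim of at least 80% power is correct.

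**The cells are the Background's figures.** 0.075 × 7,833 = 587 and 0.36 × 7,833 = 2,820 (the table has 2,819).

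**Weight of the cells.** 587/678 = 87% of paraplegia events and 2,819/3,718 = 76% of respiratory events. The respiratory rate is both the lower bound and the largest term in the upper bound.

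**Removing the cells.**
- Paraplegia: (678 − 587)/(10,310 − 7,833) = 91/2,477 = 3.7%.
- Respiratory failure: (3,718 − 2,819)/(12,191 − 7,833) = 899/4,358 = 20.6%.

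**Keeping the source with only a fraction f of its events qualifying (an assumption).** Paraplegia = (91 + 587f)/10,310; respiratory failure = (899 + 2,819f)/12,191.

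The same rule gives the table below. Power is for 46 subjects at a 26% device rate, tested against the midpoint in that row.

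| Scenario | Range | Midpoint | Success at | Power |
|---|---|---|---|---|
| Spinal cell dropped | 30.5%–74.5% | 52.5% | ≤17 | 96% |
| Respiratory cell dropped | 20.6%–67.5% | 44.1% | ≤13 | 70% |
| Both dropped | 20.6%–64.6% | 42.6% | ≤12 | 58% |
| 85% of both cells qualify | 27.0%–73.0% | 50.0% | ≤15 | 88% |
| 75% qualify | 24.7%–70.2% | 47.4% | ≤14 | 80.5% |
| 50% qualify | 18.9%–63.0% | 40.9% | ≤11 | 45% |

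**Error rate if the goal is too high.** Suppose the true open-repair MAE rate were 42.6%. The rule of 15 or fewer events in 46 would then declare success for a device with that same rate with probability P(X ≤ 15 | n = 46, p = 0.426) = 11%, against the nominal 2.5%.

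**The case against.** The strongest reply is that the proven part does not move the goal. Dropping the spinal cell alone leaves a midpoint of 52.5%, still above 50%. Everything beyond that depends on the respiratory cell, whose source definition cannot be seen. Nor is 36% out of line with the table, where two other rows give respiratory failure of 45.1% and 42%. This stands, and it limits what can be claimed.

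Deleting one row also does not align the rest. The other rows' definitions are equally unseen, and the 1,678-patient row then becomes 1,678/4,358 = 39% of the respiratory denominator and 1,678/2,477 = 68% of the paraplegia denominator. Without that row too, the rates would be (899 − 124)/(4,358 − 1,678) = 28.9% and (91 − 16)/(2,477 − 1,678) = 9.4%. This also stands: 20.6%–64.6% depends heavily on which rows remain.

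There are considerations in the other direction. The Background says that published open-repair results come from low- to moderate-risk patients and would be worse at higher risk, and the goal was set about 4 points below the 53.9% midpoint. A reader might infer from the relabelling that the goal is biased upward by a known amount and should be about 43%. The documents do not support that, because neither the pulmonary definition nor the net direction is established. At the anticipated 26%, the expected count of 0.26 × 46 = 12 would also just pass the 12-event cut-off that goes with a 42.6% goal.

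None of this justifies the relabelling or the word conservative. A similar percentage is not a matching definition, and the 4-point margin is used up once more than about 15% of the source's events in the two cells fall outside the trial's definitions.

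**Conclusion.** The point holds as a definition mismatch that leaves the description of the goal unsupported. By the protocol's own definitions the spinal entry is broader than the trial's paraplegia. The pulmonary entry is not shown to match the trial's respiratory failure. Together they dominate two columns of Table 6, and one of those columns fixes the lower bound of the range.

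The size is uncertain and almost all of it comes from the respiratory cell. The midpoint runs from 52.5% (spinal cell dropped) to 42.6% (both dropped), or from 50.0% to 40.9% if between 85% and 50% of the source's events qualify. Power of 46 subjects against the recomputed midpoint lies between 96% and 45% over these scenarios. All of them assume that the other rows' definitions are acceptable, which the documents do not show. They are sensitivity figures, and 20.6%–64.6% is not a like-for-like estimate of open-repair risk. The stated power against a 50% goal is not in error.

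**What to change.** 1. Re-extract the two cells from the source against the trial's definitions of paraplegia and respiratory failure. If the source reports no matching figures, remove them.
2. Show the Table 6 range, its midpoint and the exact power of 46 pooled subjects with and without these cells.
3. Unless re-extraction supports it, delete the word conservative and state that the 50% goal may lie above a definition-matched midpoint.
4. Leave any change of the goal to agreement across the pooled physician-sponsored studies. The hypothesis and the 46 subjects belong to the pooled data, and a change at this 16-patient site alone would split the test.
5. Add a supportive 30-day MAE rate in which paraplegia or paraparesis counts. Both are already collected.

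Items 1 to 3 and 5 need an amendment to the text and to Table 6, and no extra patients. The cost is that the stated range, and possibly the power, look less favourable. If the pooled studies did move the goal to about 42.6%, 80% power at a 26% rate would need about 67 to 72 subjects instead of 46.

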4.5.2 Mitigation of Risks

Significant care and thought has gone into designing the Valiant Thoracoabdominal Stent Graft System and investigational procedure for proper delivery and deployment of devices to minimize risks to patients to the greatest degree possible. The design of the stent graft is bifurcated to provide flow to uninterrupted blood flow to the visceral and infrarenal segments during the repair process, negating the need for aortic clamping utilized in open repair. Additionally, the design of the stent graft system is modular to allow for bailouts and staging of the procedure throughout device deployment. At any point in the procedure, the patient still has the opportunity for alternative treatments such as open surgical repair or other endovascular techniques.

All efforts will be made to minimize the identified risks including:

- Adherence to eligibility criteria and screening procedures to ensure that appropriate patients are selected and enrolled.

- Adherence to the investigation protocol and clinical methods for case planning, device modification, and implantation will be followed.
- Patients will be carefully monitored throughout the study period.
- The investigator will evaluate the adverse events during the course of the study.

Monitoring Procedures

Study monitoring and auditing will be performed by experienced and appropriately trained personnel appointed by the sponsor/investigator to ensure that the investigation is conducted in accordance with FDA IDE regulations through the Johns Hopkins Office of Human Subjects Research (OHSR). Compliance Monitoring Specialists of the Johns Hopkins OHSR will conduct a monitoring visit for investigators holding an IDE to determine compliance with sponsor requirements in 21 CFR 812 before initiation of research.

On-site monitoring for the study will be conducted and will be a continuous, interactive process to ensure that high-quality data are obtained in compliance with the clinical investigational plan and regulatory requirements. A comprehensive review of case report forms will be performed to check for completeness and accuracy. Accuracy of data reported on CRFs will be verified by comparison to source documents. On-site monitoring will be frequent enough to assure continued acceptability of the data. Monitoring will occur at the following intervals: prior to the start of the clinical trial, at initiation of the study (at first implant and shortly thereafter with more frequent and intensive monitoring at the beginning of the study), at quarterly and/or interim periods and upon completion of the clinical study. The monitor will oversee the progress of the investigation and may be an employee of the sponsor.

Informed Consent

- Review 100% of all informed consents to ensure:
- That the subject signed and dated the informed consent form for him/herself.
- A valid (current IRB-approved version) copy of consent form was used.
- Review documentation of informed consent process.

Protocol

- Confirm that the study staff is conducting the study in compliance with the protocol approved by the IRB.

Source Document Verification

- Review first five subject charts for:
- Trial eligibility. If there are any subjects that did not meet trial eligibility, then five additional charts will be monitored. These additional charts will be chosen randomly.
- Primary and secondary safety and efficacy data- If there are discrepancies/errors discovered with reporting this data, then five additional charts will be monitored. These additional charts will be chosen randomly.
- Any correction made to the source documents is dated, initialed, and explained. The original entry should not be obscured.
- The protocol specific source documents are on file.
- Source documents are completed in ink.

- Note to files are made for missing or incomplete data and to explain any discrepancies or additional comments.

Electronic Case Report Forms and Electronic Data Capture

Ensure the data reported on the eCRF is consistent with the source documents.

- Discrepancies between the source documents and eCRF are explained in a note to file or captured in a comment in the eCRF.
- Study team members will have access to Sanford's electronic data capture system (EDC) and will export de-identified data originating from JHU to this centralized database which is hosted by NAMSA.

Sanford's central EDC was originally set-up as a data pooling mechanism to fulfil a CMS reimbursement requirement for parallel IDE sites using the same investigational device. Sanford is leading the effort now to aggregate de-identified data from each independent IDE site. Sites can only access their specific data.

NAMSA: Services provided by NAMSA includes EDC access and data table generation for annual progress reports to the FDA and interim analysis reports for DSMB meetings or any instances where patient safety signals may trigger an interim analysis or pooled data analysis for DSMB review.

Sanford and Medtronic will have read-only access and will not have the ability to modify/edit eCRFs.

Adverse Events & Serious Adverse Events

- Monitor will review all subject research chart and medical records to ensure the following:
- All AEs and SAEs have been reported including any abnormal physical exam findings determined to be clinically significant.
- They have been reported in a timely manner defined as within ten (10) business days between the time the site staff became aware of the event to the time it has been recorded and entered in eCRF.
- AEs have been reviewed; attribution has been assigned and signed by investigator in a timely manner.
- Ensure any AEs and SAEs have been submitted to the IRB and FDA that meets IRB/FDA reporting criteria.
- All subject deaths have been reported appropriately.

Protocol Deviations

- Ensure all protocol deviations that meet reporting requirements have been reported to the IRB as well as reported in eCRF.

Investigational Product

- Ensure investigational product has been properly handled and stored.

Reporting

All reports to FDA will be identified as SI-IDE Reports:

Deviations from the investigational plan: The sponsor-investigator will notify the reviewing IRB and FDA of any deviation from the investigational plan to protect the life or physical well-being of a subject in an emergency. The notice will be provided as soon as possible but no later than 5 working days after the emergency occurred. If the change or deviation may affect the scientific soundness of the investigational plan or the rights, safety or welfare of the subject, the sponsor will obtain prior IRB approval and also FDA approval for the deviation by submitting an IDE supplement.

Unanticipated adverse device effects: The sponsor-investigator will report the results of an evaluation of an unanticipated adverse device effect to FDA and all reviewing IRBs within 10 working days after the sponsor-investigator first receives notice of the adverse effect.

Withdrawal of IRB approval: The sponsor-investigator will notify FDA of the withdrawal of IRB approval of an investigation (or any part of an investigation) within 5 working days of receipt of the withdrawal of approval.

Progress report or annual reports: The sponsor will provide progress reports to all reviewing IRBs and to the FDA using the suggested format provided at:

<http://www.fda.gov/MedicalDevices/DeviceRegulationandGuidance/HowtoMarketYourDevice/InvestigationalDeviceExemptionIDE/ucm046717.htm#sugforforidefin>

To describe the follow-up compliance for the study, the sponsor will include a table in the annual progress report.

Interim Reporting: As requested by the FDA, the sponsor will report at intervals of every five patients treated under the IDE regardless of study arm. The interim report will be submitted within ten days following the 30-day follow-up of the fifth patient enrolled.

Recalls and device dispositions:

The sponsor-investigator will notify FDA and all reviewing IRB's of any request that a sponsor-investigator return, repair, or dispose of any unit of an investigational device. The notice will be made within 30 working days after the request is made and will state why the request was made.

Final report:

The sponsor-investigator will notify FDA and all reviewing IRBs within 30 working days of the completion or termination of the investigation. The sponsor-investigator will also submit a final report to FDA and all reviewing IRBs and participating investigators within 6 months after the completion or termination of the investigation. The suggested format for final IDE reports will be utilized in preparing the final report as described at:

<http://www.fda.gov/MedicalDevices/DeviceRegulationandGuidance/HowtoMarketYourDevice/InvestigationalDeviceExemptionIDE/ucm046717.htm#sugforforidefin>

Clinical Trial Database report:

The sponsor-investigator with an applicable study registered with the National Institutes of Health (NIH) National Library of Medicine's (NLM) ClinicalTrials.gov will report results of the study within 12 months of the trial reaching its completion data regardless of outcomes or if the study is terminated early.

Failure to obtain informed consent:

The sponsor-investigator will submit a report of the use of a device without first obtaining informed consent. The report will be made to FDA within 5 working days after receipt of the notice of such use.

Other reports:

The sponsor-investigator will provide accurate, complete, and current information about any aspect of the investigation upon request from the reviewing IRB or FDA.

Data and Safety Monitoring

This study will have oversight by Sanford Data Safety Monitoring Board (DSMB) consisting of independent scientific and bio-statistical expertise, who are not participating as investigators in the study. Sanford is an integrated healthcare system comprised of hospitals, physicians, and other healthcare providers and facilities located in Sioux Falls, SD. The Sanford DSMB will comprise at least 1 physician experienced in treating the study population and an independent biostatistician (including NAMSA statistical support). The Sanford DSMB will work with the PI to monitor and evaluate the safety of subjects and progress of the study. The board will meet after every 5th patient receiving the investigational device and annually during the follow-up period to review subject data. The board will also meet at unscheduled times according to clinical necessity. The data safety reports reviewed at each meeting will contain enrollment data and all documented adverse events experienced by the participants and treatment outcomes. The focus of the analysis is to determine whether enrollment should continue or be closed and whether the trials should continue as originally designed or require modification/amendment.

Definitions

Aortic aneurysm enlargement: ≥ 5 mm as compared to any previous CT measure using orthogonal (i.e., perpendicular to the centerline) measurements

Aortoiliac aneurysm: aneurysm of the abdominal aorta and including one or both of the iliac arteries

Aneurysm-related mortality:

Death occurring within 30 days or during hospitalization following the index procedure, unless there is evidence of accidental or self-inflicted death;

Death occurring within 30 days or during hospitalization following conversion to open repair or a secondary intervention for migration, Type I and III endoleaks, device integrity failure (e.g., fracture), or patency-related events (i.e., device stenosis or occlusion and embolic events), unless there is evidence of accidental or self-inflicted death;

Death occurring within 30 days or during hospitalization for a complication of the aneurysm or a complication associated with the device, such as:

- aortic rupture
- fistula formation (e.g., aorto-enteric)
- embolization
- malperfusion of organ(s) or limb(s)

Arterial fistula formation: formation of an abnormal connection or passageway between an artery and adjacent structures

Conversion to Open, Early: any open repair within 30 days of the index procedure involving the vasculature in the abdomen and/or pelvis.

Conversion to Open, Late: any open surgical repair involving stentgraft removal after 30days post index procedure

Chronic Obstructive Pulmonary Disease (COPD): forced expiratory volume (FEV1) < 1.0 liter or receiving home oxygen

Crawford Type IV TAAA: aneurysmal dilatation originating within 5cm of the celiac artery

Disabling stroke: Modified Rankin Score MRS >2

Distal landing zone: aortic fixation site furthest from the heart

Embolization: dislodging of an upstream particle that travels downstream causing blockage of free flow further downstream. Embolization could result in malperfusion

Embolus: blood clot that forms at one location (presumably from the aneurysmal sac, aortic neck, or adjacent vessels) and is dislodged to another location resulting in ischemic changes

Emergent: an aneurysm requiring immediate treatment

Endoleak:

Type I: leak occurring at the proximal or distal fixation site, including leakage around fenestrations

Type Ia: leak occurring at the proximal fixation zone of the stent-graft

Type Ib: leak occurring at the distal fixation zone of the stent graft

Type Ic: leak occurring at the distal fixation zone of the covered stents in the visceral vessels incorporated by the fenestrations

Type II: leak caused by retrograde flow from patent lumbar or inferior mesenteric arteries

Type IIIa: leak caused by a defect in the graft fabric

Type IIIb: leak caused by inadequate seal between modular graft components

Type IV: leak caused by graft fabric porosity, often resulting in a generalized blush of contrast within the aneurysm sac

Type V: aneurysm enlargement without visualized leak

Endoleak, Early: any endoleak observed within 30 days after device deployment

Endoleak, Late: any endoleak observed later than 30 days after deployment that was not documented during the first 30 days after deployment

Estimated Glomerular Filtration Rate (eGFR): estimated GFR (mL/min/1.73 m²) = 175 x (Serum creatinine)^{-1.154} x (Age)^{-0.203} x (0.743 if female) x (1.210 if African-American)

Graft Relining: placement of the investigational system that results in landing zones that extend beyond the limits of the previously placed graft material

Limb occlusion: the presence of thrombus within any graft limb that creates occlusion

Major adverse events: all-cause mortality, bowel ischemia (requiring medical or surgical management), myocardial infarction, paraplegia, renal failure, respiratory failure, and stroke

- **All-Cause Mortality:** any death occurring within the first 30 days post procedure
- **Bowel Ischemia:** Bowel ischemia due to limb or arterial occlusion, graft placement, or embolization.
- **Myocardial infarction:** raised levels of cardiac biomarkers or ECG changes
- **Paraplegia:** spinal cord ischemic event resulting in complete loss of motor function with or without loss of sensation in the lower extremities
- results in a serum creatinine >2.0 mg/dl that does not spontaneously resolve
- **Renal Failure:** acute or progressive renal insufficiency leading to the need for dialysis or hemofiltration
- **Respiratory failure:** ventilator support >24 hours after spinal drain removal and/or reintubation. This definition does not put the patient at any increased risk. The high risk patient population being treated in this study is prone to pre-existing comorbidities, including COPD and decreased respiratory function, and may require extended ventilator support while in the supine position for spinal drainage.
- **Stroke:** neurological deficit that lasts > 24 hours

Malperfusion of organ(s) or limb(s): loss of flow through a particular vascular bed has been partially or completely compromised leaving the said organ or limb ischemic

Migration, clinically significant: antegrade or retrograde migration that requires surgical or endovascular intervention

Paraparesis: spinal cord ischemic event resulting in partial neurologic deficit in the lower extremities

Parietal arteries (branches): inferior phrenic, lumbar and middle sacral arteries

Patency: the state of a vessel that has unimpeded flow into and out of the vessel

Proximal landing zone: the aortic fixation site closest to the heart

Proximal fixation length: the aortic fixation site measured from the proximal edge of the graft to the start of the aneurysm

Renal insufficiency: rise in serum creatinine of more than 50% above pre-procedure level which results in a serum creatinine >2.0 mg/dl that does not spontaneously resolve

Technical success:

- successful delivery (i.e., ability to deliver the implant to the intended implantation site, without the need for unanticipated corrective intervention related to delivery);
- successful and accurate deployment, defined as:
 - deployment of the endovascular stent-graft at the intended implantation site;
 - patency of all endovascular graft and stent components; absence of device deformations (e.g., kinks, stent eversion, mal-deployment, misaligned deployment) requiring unplanned placement of an additional device;
 - absence of inadvertent covering of aortic branch vessels; and
- successful withdrawal (i.e., successful withdrawal of the delivery system, without need for unanticipated corrective intervention related to withdrawal)

Thrombus: a blood clot that forms due to injury of a vessel. If the thrombus becomes dislodged and travels it is referred to as an embolus

Treatment success: a composite of technical success and freedom from the following:

- aneurysm enlargement i.e. >5-mm as compared to any previous CT measuring orthogonal (i.e., perpendicular to centerline) measurements
- aneurysm-related mortality
- aneurysm rupture
- conversion to open repair
- secondary intervention for migration, type I and III endoleaks, device integrity failure (i.e., fracture), and patency-related events (i.e., device stenosis or occlusion and embolic events)
- Renal failure

Type B – Chronic Dissection: a dissection that takes off distal to the left subclavian artery that is greater than 30 days old

Type B – Subacute Dissection: a dissection that takes off distal to the left subclavian artery that is 15-30 days old

Urgent: An aneurysm requiring repair within 1 week

Visceral arteries (branches): celiac, superior mesenteric, inferior mesenteric, renal arteries

9. Benefits

- a. Description of the probable benefits for the participant and for society.
To find potential benefits after complex aortic surgery for patient outcomes and health.

10. Payment and Remuneration

- a. Detail compensation for participants including possible total compensation, proposed bonus, and any proposed reductions or penalties for not completing the protocol.

Participants will not receive payment/remuneration.

11. Costs

- a. Detail costs of study procedure(s) or drug (s) or substance(s) to participants and identify who will pay for them.

There is no cost to participate in the study. The procedures are covered under guidelines for Medicare/Medicaid in the standard delivery of care.

Medicare Generalizability

